2.1. Hypotheses

The efficacy of the recombinant, adjuvanted herpes zoster vaccine (Shingrix®) is high. We hypothesize that early innate signatures of vaccination should correlate with responses to, and predict the immunogenicity of, Shingrix® in older adults, independently of age.

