4.2. Inclusion Criteria

1. Subject must be able to understand and provide informed consent.
2. Adults aged 50-60 years, or community dwelling adults aged 70 years and above.

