13.4 Analysis Plan

Data from the study will be analyzed using the statistical software R. High-throughput data will be analyzed using appropriate methods, either by stand-alone software or modules in leading statistical software, e.g. the Bioconductor in the R framework. For cytokine data, missing values will be dealt with using multiple imputations. For gene expression and metabolomics data, nearest neighbor method and local least squares may be used to fill missing values. Unsupervised learning techniques such as PCA, PLSDA, clustering, and factor analysis will be used for the visualization and identification of global patterns. For descriptive endpoints, we will generate summary statistics, and visualize the data using histograms and boxplots when applicable. For the identification of innate signatures, the two age groups will be analyzed separately.

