13.4.5 Analyses of Exploratory Endpoint(s)/Outcome(s)

Exploratory Endpoint 1. The innate immune response signatures are identified from traditional immune parameters, gene expression measured by RNA-seq experiment, and metabolomics data measured by LC/MS. The innate signatures will be identified for the two age groups separately. The traditional immune parameters, genes, and metabolites that change significantly over baseline after immunization are considered innate signatures.

Traditional markers will be tested using paired t-test or Wilcoxon test against D0, and significant markers will be considered part of the innate immune signature.

RNA-seq data will be preprocessed using Bowtie and Tophat, and FPKM (fragments per kilobase of exon model per million mapped reads) values will be calculated. Gene level comparison of D1, D4, D14 and D30 vs D0 will be conducted using DESeq to find the transcriptomics signature of vaccination.

Metabolomics data will be processed using packages apLCMS, XCMS, and xMSAnalyzer and generate data tables containing accurate mass m/z , retention time(s), intensity, coefficient of variation, and

related descriptive characteristics, including minimal information standards for metabolomics data. SAM(8) and similar methods will be used to detect differential abundance of features between D1, D4, D14 and D30 vs D0 to select metabolic innate signatures.

After each vaccination, the innate signatures that are correlated with the D30 antibody titers are considered correlation signatures of the innate immune responses. The correlation will be assessed using Spearman's correlation and the associated p-values.

Exploratory Endpoint 2. We will use paired t-test or Wilcoxon test to compare each immune parameter (changes in phenotype of T cell responses and the kinetics of these changes) between D7, D14 and D30 after vaccination and D0 for each dose of Zoster vaccine.

Exploratory Endpoint 3. We will use paired t-test or Wilcoxon test to compare each immune parameter (changes in the magnitude of activated B cells, antibody secreting cells and memory B cells and the kinetics of these changes) between D7, D14 and D30 after vaccination and D0 for each dose of Zoster vaccine.

Exploratory Endpoint 4. We will use paired t-test or Wilcoxon test to compare VZV serology between D14, D30, D180 and D270+ (optional visit) after vaccination and D0 for each dose of Zoster vaccine.

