13.7 Sample Size Considerations

For sample size consideration, we will use the alpha level of 0.01 for the immune parameters. Given less than 50 immune parameters will be tested, this alpha level translates to an expected count of false positives of <1, which is an acceptable level. For the gene expression data and for sample size consideration only, we will use the alpha level of 0.0005 to offset the effect of multiple testing. This means an average of one false positive for every 2000 null genes tested; given ~20,000 genes will be measured, this alpha level translates to an expected 10 false positives. We expect >100 genes will be truly differentially expressed. Thus among all genes called differentially expressed, the proportion of false positives will be <10%, which is an acceptable level in gene expression studies. We note this consideration is for sample size analysis alone. In actual data analysis false discovery rate (FDR) will be used.

For the traditional immune parameters, with 30 samples in a treatment group, we can reject the null hypothesis of equal means with 80% power if the true effect size (mean difference/sigma) is 0.66, using a two-sided paired t-test and the alpha level of 0.01. For the gene expression, the actual data analysis will be performed using the false discovery rate. For simplicity, for sample size consideration, we will consider the simpler case of a paired t-test. With 30 samples in a treatment group, we can reject the null hypothesis of equal means with 80% power if the true effect size (mean difference/sigma) is 0.88, using a two-sided paired t-test and the alpha level of 0.0005.

For unpaired test, with sample size of 30 per group, at the alpha level of 0.01, we can reject the null hypothesis of equal means with 80% power if the true effect size ((mean0-mean1)/sigma, assuming equal variance) is 0.91 using an unpaired two-sided t-test.

For a paired t-test, with the sample size of 30, at the alpha level of 0.01, we can reject the null hypothesis of no change with 80% power if the true effect size (mean difference/sigma) is 0.66.

For correlation analysis, with 30 samples in the treatment group, at the alpha level of 0.01, we can reject the null hypothesis of zero correlation with 80% power if the true correlation is 0.57 using a two-sided test for Pearson's correlation coefficient.

14. Identification and Access to Source Data

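### Correlation signatures are declared from unadjusted Spearman tests, so a marker linked to the D30 titre only through age within the ≥70 cohort, or only through sex, can be called a signature

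*Combined protocol and SAP*

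**What the plan says.** Section 13.4.5, Exploratory Endpoint 1, works in two steps. Immune parameters, genes and metabolites that change significantly from baseline become innate signatures. Then, after each vaccination, "the innate signatures that are correlated with the D30 antibody titers are considered correlation signatures of the innate immune responses". The test is given in one sentence: "The correlation will be assessed using Spearman's correlation and the associated p-values". No covariate is named in that rule or anywhere else in section 13.

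Age is handled by splitting the sample. Section 13.4 states "For the identification of innate signatures, the two age groups will be analyzed separately", and 13.4.5 repeats "The innate signatures will be identified for the two age groups separately". Both sentences concern finding innate signatures; the correlation sentence does not say whether it too is run by cohort. The sizing in 13.7 suggests that it is, because it uses the size of one cohort: "For correlation analysis, with 30 samples in the treatment group, at the alpha level of 0.01".

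The cohorts are set by section 4.2: "Adults aged 50-60 years, or community dwelling adults aged 70 years and above". The younger group spans about ten years and the older has no ceiling. Section 2.1 hypothesises that early innate signatures correlate with responses and "predict the immunogenicity of, Shingrix® in older adults, independently of age". Demographic data are collected at screening (section 8.2 and Appendix D).

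**The concern.** A zero-order correlation cannot tell a marker of vaccine response from a marker of ageing when both the marker and the titre move with age in the people analysed. The cohort split deals with 50-60 versus ≥70. It does nothing about a 71-year-old and an 85-year-old in the same cohort, should both be enrolled, or about men and women in either cohort.

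This matters because the plan's hypothesis is worded as independence from age, and section 1.1 also wants these signatures to shed light on age-related immune defects. A signature produced by shared dependence on age would be read as support for that hypothesis when it is not. The primary endpoint is not affected; what is at stake is the interpretation of an exploratory result tied to the central hypothesis.

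**Working it through.** **Inputs from the documents.** n = 30 per cohort, two-sided alpha 0.01, 80% power, detectable correlation 0.57 (13.7); unadjusted Spearman (13.4.5); no upper age limit in the older cohort (4.2).

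**Assumed inputs.** The documents give no correlation of age with any marker or with the titre, and no age distribution within the older cohort. Both age correlations are therefore set to a common value *a*, varied from 0.3 to 0.8, with age either normal or right-skewed (exponential).

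**1. The plan's own figure.** Section 13.7 claims detection "with 80% power if the true correlation is 0.57 using a two-sided test for Pearson's correlation coefficient". By Fisher's z, the detectable r = tanh[(2.576 + 0.842)/√(30 − 3)] = 0.577. Power at 0.57 is 78.5% by Fisher's z, 80.0% with the bias term r/[2(n − 1)], and 79.2% with a t-based critical value. The stated figure reproduces. A sample correlation of about 0.46 is needed for p < 0.01.

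**2. What shared dependence on age induces.** If marker and titre are independent given age, their correlation is a × a: 0.09, 0.16, 0.25 and 0.36 for a = 0.3, 0.4, 0.5 and 0.6.

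**3. How often such a pair is flagged.** Simulation with 20,000 runs per setting, n = 30, alpha 0.01, no direct marker-titre link:

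| a | induced r | plain Spearman, normal / skewed age | partial Spearman given age, normal / skewed |
|---|---|---|---|
| 0.3 | 0.09 | 2.0% / 1.9% | 1.1% / 1.2% |
| 0.4 | 0.16 | 3.6% / 3.1% | 1.1% / 1.1% |
| 0.5 | 0.25 | 9.1% / 7.1% | 1.0% / 1.2% |
| 0.6 | 0.36 | 23% / 16% | 1.2% / 1.4% |
| 0.7 | 0.49 | 52% / 33% | 1.4% / 1.7% |
| 0.8 | 0.64 | 87% / 63% | 1.6% / 2.0% |

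The partial test holds the rate close to nominal through a = 0.6 and drifts up slightly beyond that.

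**4. A stricter cut-off.** At alpha 0.0005, the value that 13.7 uses to size the gene-expression tests, plain Spearman flags about 1% at a = 0.5. That is lower, but still about 0.01/0.0005 = 20 times the nominal level. At a = 0.7 it flags 19% (normal age) or 9% (skewed).

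**5. Sex.** With equal numbers of each sex, and marker and titre both differing between the sexes by *d* within-sex SDs, the induced correlation is d²/(d² + 4): 0.14, 0.20 and 0.26 for d = 0.8, 1.0 and 1.2. Plain Spearman flags about 3.5%, 6.5% and 13%; adjustment for sex returns the rate to about 1%. These differences are also assumed.

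**6. If the correlations were pooled over cohorts.** At n = 60 and a = 0.5, plain Spearman flags 23% at alpha 0.01. Whether the test is run within cohort therefore needs to be stated.

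**7. Cost of adjustment.** Replacing n − 3 by n − 3 − k in step 1, the detectable r rises from 0.577 to 0.585 with age (k = 1) and to 0.594 with age and sex (k = 2). Power at a partial correlation of 0.57 falls from 79% to 77% and 75% (t-critical version).

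That holds the partial correlation at 0.57. If 0.57 is instead the unadjusted correlation, the partial correlation given age is (0.57 − a²)/(1 − a²): 0.48/0.91 = 0.53 at a = 0.3, and 0.21/0.64 = 0.33 at a = 0.6. Fisher-z power with two covariates is then about 64% and 19%, against 78.5% unadjusted. Part of that drop is confounding being removed.

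**The case against.** The case for leaving the plan as it is has real content.

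- **Size.** A reader might infer that any marker and titre that merely track age will be reported as a signature. The table does not support that. For age correlations of 0.3 to 0.6, at least 77% of such pairs are not flagged. Flagging becomes more likely than not only near 0.7 with normal age, or nearer 0.8 with skewed age.
- **Age span.** No upper limit does not prove a wide spread among 30 generally healthy, community-dwelling volunteers. The documents also do not show that false signatures would gather in the older cohort.
- **Pre-screen.** Only markers that change after vaccination reach the correlation step, so a static marker of ageing should not get there. This narrows the candidates but leaves age confounding among markers that do respond.
- **Alpha.** The 0.01 level is a sizing value, and 13.7 announces FDR control for the actual analysis. Whether that covers the correlations is unclear. If it does, the rates above are not those of the planned analysis. FDR guards against chance, however, and a correlation induced by age is a real non-zero association.
- **Meaning of the hypothesis.** Independence from age can be read as holding in both age groups, which separate analysis partly addresses. Sections 1.1 and 13.6 also speak of prediction, for which an unadjusted correlation is a legitimate quantity. A reader might conclude that plain Spearman is an error and must be replaced; that is a choice of estimand, and the documents do not settle it.
- **Sex.** No sex effect on marker or titre is documented. Section 1.1 lists female sex only as a risk factor for zoster.
- **Flexibility.** The closing paragraph of 13.4.5 allows ad hoc alternatives, but it names no adjustment, and a post hoc choice is weaker than a prespecified one.

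These points limit the size of the concern and the strength of the remedy. They do not supply the missing control for age within the older cohort.

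**Conclusion.** The concern holds in a limited form. Correlation signatures are declared from unadjusted tests; the cohort split removes the contrast between cohorts; age within the open-ended cohort and sex in both stay uncontrolled. A marker and titre linked only through one of these can be called a signature, so the plan as written cannot show that a signature is independent of age in the within-cohort sense.

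The inflation is modest at age correlations of 0.3 to 0.4 and substantial from about 0.6. All these rates rest on assumed correlations, a per-test alpha taken from the sizing, and equal age dependence of marker and titre; the sex figures rest on assumed differences. The planned Spearman test can stay. What is missing is an adjusted analysis beside it and a rule for when independence from age may be claimed. The sponsor should add both.

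**What to change.** In section 13.4.5, Exploratory Endpoint 1:

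1. State that the correlations with the D30 titre are run within each age cohort.
2. Prespecify a partial Spearman correlation between each innate signature and the D30 titre, adjusted for age in years and sex, and report it beside the planned unadjusted Spearman.
3. Describe a signature as independent of age only if it holds in the adjusted analysis.
4. Say whether the FDR control announced in 13.7 applies to these correlations.

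No new data are needed; the change is SAP wording and a small addition to the code. The statistical cost is two degrees of freedom in the adjusted analysis, with the loss of power shown in step 7 of the working. The loss is larger for a marker whose unadjusted correlation is partly due to age, which is one reason to keep the unadjusted coefficient in view.

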13.2 Endpoints

Primary Endpoint

- Differences in innate immune signatures between D0, D1, and D7 and each dose of Zoster vaccine recombinant, adjuvanted, in both age cohorts.

Secondary Endpoint

- Differences in related adverse events and serious adverse events between each dose of Zoster vaccine recombinant, adjuvanted, in both age cohorts.

Exploratory Endpoints

- The changes in transcriptomics, metabolomics and immune cell populations between D0 (before vaccination) and D1, D3, D7, D14 and D30 after each dose of Zoster vaccine recombinant, adjuvanted, in both age groups
- The changes in the phenotype of T cell responses and the kinetics of these changes between D0 (before vaccination) and D7, D14 and D30 after each dose of Zoster vaccine recombinant, adjuvanted, as well as D180 and D270+ (optional visit) in both age groups.
- The changes in the magnitude of activated B cells, antibody secreting cells and memory B cells and the kinetics of these changes between D0 (before vaccination) and D7, D14 and D30 after each dose of Zoster vaccine recombinant, adjuvanted, as well as D180 and D270+ (optional visit) in both age groups.
- The changes in VZV serology between D0 (before vaccination) and D14 and D30 after each dose of Zoster vaccine recombinant, adjuvanted, as well as D180 and D270+ (optional visit) in both age groups.
- The changes in specificity, magnitude and phenotype of VZV-specific (gE and other antigens) T cells and the kinetics of these changes between D0 (before vaccination) and 7, 14, 30 days after each dose of Zoster vaccine recombinant, adjuvanted, and at D180 and D270+ (optional visit) in both age groups.
- The changes in magnitude of VZV-specific B cells and the kinetics of these changes between D0 (before vaccination) and 7, 14, 30 days after each dose of Zoster vaccine recombinant, adjuvanted, and at D180 and D270+ (optional visit) in both age groups.
- Baseline stool microbiome alpha and beta diversity parameters.

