Exploratory Endpoint 5. We will use paired t-test or Wilcoxon test to compare each immune parameter (changes in specificity, magnitude, and phenotype of VZV-specific T cells and the kinetics of these changes) between D7, D14, D30, D180 and D270+ (optional visit) after vaccination and D0 for each dose of Zoster vaccine.

Exploratory Endpoint 6. We will use paired t-test or Wilcoxon test to compare each immune parameter (changes in magnitude of VZV-specific B cells and the kinetics of these changes) between D7, D14, D30, D180 and D270+ (optional visit) after vaccination and D0 for each dose of Zoster vaccine.

Although our statistical methods will adhere to what is proposed herein, our experience with analyses of similar studies in the past has underscored the need for flexibility and adaptability in trying different statistical approaches to arrive at the most informative results. As such, we may use alternative approaches such as the gene set enrichment analyses, or other approaches, in an *ad hoc* basis.

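### The planned analyses of Exploratory Endpoints 2 and 3 stop at D30 after each dose, although both endpoints are defined through D180 and D270+

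*Combined protocol and SAP*

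**What the plan says.** Section 13.2 defines Endpoint 2 as "The changes in the phenotype of T cell responses and the kinetics of these changes between D0 (before vaccination) and D7, D14 and D30", and Endpoint 3 as "The changes in the magnitude of activated B cells, antibody secreting cells and memory B cells and the kinetics of these changes" over the same early days. Both definitions end with the same time frame: "after each dose of Zoster vaccine recombinant, adjuvanted, as well as D180 and D270+ (optional visit) in both age groups". The Synopsis and section 3.4 give the same definitions.

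Section 13.4.5 gives the analysis. For both endpoints it is a paired t-test or Wilcoxon test of each immune parameter "between D7, D14 and D30 after vaccination and D0 for each dose of Zoster vaccine". Neither D180 nor D270+ appears.

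The next three endpoints in the same section do carry the late visits. Endpoint 4 will "compare VZV serology between D14, D30, D180 and D270+ (optional visit) after vaccination and D0". Endpoints 5 and 6 are compared "between D7, D14, D30, D180 and D270+ (optional visit) after vaccination and D0 for each dose of Zoster vaccine".

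Blood for innate and adaptive assays is scheduled at D180 and at the optional D270+ visit (section 3.1, section 8, Appendix D). Both visits are timed from the first vaccination (sections 8.4.1 and 8.6).

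**The concern.** Both endpoints include the kinetics of the changes. With the analysis as written, the last planned contrast is 30 days after the second dose, which is the D90 visit. Whether a change persists or returns to baseline between D90 and D180 or later then has no planned test for these two endpoints. Persistence is the natural question for memory B cells, which Endpoint 3 names.

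If the late contrasts are added only after the data have been seen, they become post hoc comparisons in a study that already has many parameters and time points. If they are not added, part of a defined endpoint goes unreported. Because three sibling endpoints keep the late visits and no reason is given for treating these two differently, the omission reads as a drafting slip and not a decision.

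**Working it through.** **1. Time points defined and analysed.** Each late visit is counted once, because it is a single visit timed from the first vaccination. Counts are contrasts with D0, per parameter and age group.

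| Exploratory endpoint | Defined (13.2) | Analysed (13.4.5) | Missing |
|---|---|---|---|
| 2, T-cell phenotype | 3 days × 2 doses + 2 late = 8 | 3 × 2 = 6 | D180, D270+ |
| 3, activated B cells, antibody-secreting cells, memory B cells | 3 × 2 + 2 = 8 | 3 × 2 = 6 | D180, D270+ |
| 4, VZV serology | 2 × 2 + 2 = 6 | 6 | none |
| 5, VZV-specific T cells | 3 × 2 + 2 = 8 | 8 | none |
| 6, VZV-specific B cells | 3 × 2 + 2 = 8 | 8 | none |

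**2. Does other text restore the missing contrasts?**
- The closing paragraph of 13.4.5 allows alternative statistical approaches. It concerns methods and adds no time points.
- Section 13.4.6 covers antibody titers and adverse event rates only.
- Section 13.4 promises summary statistics for descriptive endpoints, without naming Endpoints 2 or 3 or the late visits.

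None of these supplies a D180 or D270+ test for the two endpoints.

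**3. How much do the other endpoints cover?** Endpoint 5 tests "changes in specificity, magnitude, and phenotype of VZV-specific T cells and the kinetics of these changes" through D270+, so antigen-specific T-cell phenotype is covered late. Endpoint 6 does the same for the magnitude of VZV-specific B cells. Section 9 lists one memory B-cell count, and it is VZV-specific. Those data may fall under Endpoint 6, although Endpoint 6 does not name memory cells. Section 9 also lists readouts that are not antigen-specific, such as total plasmablasts and the phenotype of activated CD4 T cells. Endpoints 5 and 6 do not reach these.

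**4. What the added tests could detect.** Section 13.7 states 80% power for a two-sided paired t-test with n = 30, alpha = 0.01 and standardized effect 0.66. The exact check uses a noncentral t with df = n − 1 = 29 and noncentrality 0.66 × √30 = 3.61. It gives 79.7%, so the stated figure reproduces.

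The documents give no expected attendance at D270+, so the range of n per age group below is an assumption:

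| n with D0 and late sample | Power at effect 0.66 | Effect detectable with 80% power |
|---|---|---|
| 30 | 80% | 0.66 |
| 24 | 66% | 0.75 |
| 20 | 55% | 0.84 |
| 15 | 38% | 1.00 |
| 10 | 20% | 1.33 |

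**5. Multiplicity cost.** If 0.01, which 13.7 gives for sample-size purposes, is taken as the testing level, two more contrasts add 2 × 0.01 = 0.02 expected false positives per null parameter per age group. The total goes from 6 × 0.01 = 0.06 to 8 × 0.01 = 0.08.

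**The case against.** The strongest case on the other side is that little is lost. The exploratory T-cell and B-cell objectives in section 2.4 all concern VZV-specific cells, and Endpoints 5 and 6 follow those cells through D180 and D270+. No listed objective asks about the durability of total, non-antigen-specific populations. The endpoints are exploratory, one of the two missing visits is optional, and no primary or secondary conclusion depends on them.

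Most of this stands, and it limits the size of the point. It also rules out two stronger readings that a reader might infer. One is that the durability of T-cell phenotype and of memory B cells goes wholly untested. The documents do not support this, because the VZV-specific phenotype is tested late under Endpoint 5, and Endpoint 6 may include the VZV-specific memory cells. The other is that the late blood is never used. It serves Endpoints 4, 5 and 6.

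What the objection does not remove is the mismatch itself. Two endpoints are defined with late visits in three places, and their stated analysis leaves those visits out.

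**Conclusion.** The point holds in a limited form. For Endpoints 2 and 3, section 13.4.5 delivers six of the eight defined contrasts per parameter and age group. Without a planned late test are overall T-cell phenotype, activated B cells, antibody-secreting cells, and memory B cells as named in Endpoint 3. The primary and secondary endpoints are unaffected, and the figures in 13.7 stand.

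Three assumptions apply. Each late visit is counted once against D0. Whether VZV-specific memory B cells belong to Endpoint 6 is a reading of the assay list, since the endpoint text does not say so. The documents show that late blood is scheduled, not that it has been collected, so the low cost of the fix rests on the schedule.

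**What to change.** In 13.4.5, add to Endpoints 2 and 3 one paired contrast of D180 with D0 and one of D270+ with D0, the second among participants who attend the optional visit. State each once. The wording used for Endpoints 4 to 6 should not be copied, because it attaches the late visits to each dose although there is only one D180 and one D270+ visit per participant. Report the number of pairs at each late visit, since precision at D270+ depends on attendance.

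If the late visits were never meant for these two endpoints, the alternative is to remove them from the definitions in the Synopsis, section 3.4 and section 13.2, with a reason.

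Adding the contrasts means a wording change and two more exploratory contrasts per parameter per age group, with lower precision at D270+. It needs no new visits or blood draws. The change is best made before the late data are examined.

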2.4. Exploratory Objectives

- To assess the specificity, magnitude, kinetics or phenotype of VZV-specific (gE and other antigens) T cells of the Zoster vaccine recombinant, adjuvanted.
- To assess the magnitude, kinetics of VZV-specific B cells of Zoster vaccine recombinant, adjuvanted.
- To identify innate immune signatures that correlate with the magnitude of the adaptive immune responses to the Zoster vaccine recombinant, adjuvanted.
- To determine the differences in specificity, magnitude, kinetics or phenotype of VZV-specific (gE and other antigens) T cells to the Zoster vaccine recombinant, adjuvanted between adults ≥ 70 and 50-60 years of age.

- To determine the differences in magnitude, kinetics of VZV-specific B cells between adults ≥ 70 and 50-60 years of age to the Zoster vaccine recombinant, adjuvanted.
- To collect stool for microbiome analysis.

3. Study Design

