8.6. Visit Windows

Study visits should take place within the time limits specified below:

D0 (first dose of vaccination) D1, D3, D7 (+/-1), D14 (+/-2), D30 (+/-7), D60 (+7) (second dose of vaccine), D61, D63, D67 (+/-1 from second vaccination), D74 (+/-2 from second vaccination), D90 (+/-7 from second vaccination), D180 (+/-14 from first vaccination, for each scheduled visit. An optional visit at any time point past 9 months (D270 +) from first vaccination may also take place.

This is also indicated on the Table of Events.

9. Mechanistic Assays

1. Expression of cytokines and chemokines via FACS. This assay will detect the expression profile of cytokines and chemokines to determine the innate response to vaccination.
2. Analysis of innate immune responses using FACS to assess numbers of activated innate cell populations. This assay will detect innate cell population activation including DC subsets, monocyte subsets, and NK cells, since these cell subsets are known to play crucial roles in immune regulation.
3. Molecular signatures of vaccination using RNA-seq on 2 mL of whole blood. This assay will determine the changes in mRNA and miRNA expression in whole blood. Results will be interpreted with use the method Significance Analysis of Microarrays (SAM) to determine change over baseline.
4. Microbiome Analysis: Analysis of microbiome diversity in the stool samples will be performed by Illumina MiSeq V4 16S Sequencing. Sample preparation will involve quantification and normalization of genomic DNA, PCR amplification of V4 hypervariable region of the bacterial 16S rDNA gene, PCR product quantification and library construction. Illumina MiSeq V4 16S sequencing and Bioinformatics analysis will involve V4 hypervariable region paired-end amplicon sequencing (MiSeq: 2x250 cycles). Filtering and trimming of all sequencing data will be done and mapped to taxonomic databases to identify bacterial composition in samples.
5. Levels of VZV-specific IgG/IgA/IgM antibody titers in the plasma by ELISA. This antibody assay will be used to quantify the levels of VZV-specific IgG and IgA in the plasma. Positive results will be assessed by 2X the negative control wells.
6. Number of VZV-specific IgG/IgA/IgM plasmablasts via ELISPOT. This cellular assay will be used to quantify the number of VZV-specific and total IgG/IgA/IgM antibody secreting cells in the blood. Positive results will be assessed by > 5 spots per million PBMCs.

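### Two exploratory objectives ask for age differences in VZV-specific T and B cells, but 13.4.5 assigns Exploratory Endpoints 5 and 6 only paired tests against D0, and the two-group test sized in 13.7 is never assigned to them.

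*Combined protocol and SAP*

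**What the plan says.** Section 2.4 (Exploratory Objectives) contains two objectives that compare the age cohorts. One is "To determine the differences in specificity, magnitude, kinetics or phenotype of VZV-specific (gE and other antigens) T cells" between adults aged 70 and above and adults aged 50-60. The other is "To determine the differences in magnitude, kinetics of VZV-specific B cells between adults" of the same two age ranges. They stand apart from the first two exploratory objectives, which only assess the response to the vaccine.

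Section 13.2 (Endpoints) defines the matching endpoints, for each cohort, by the comparison "between D0 (before vaccination) and 7, 14, 30 days after each dose of Zoster vaccine recombinant, adjuvanted, and at D180 and D270+ (optional visit"). That is a change from baseline, not a contrast between groups.

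Section 13.4.5 gives Exploratory Endpoints 5 (T cells) and 6 (B cells) a paired t-test or Wilcoxon test. For B cells it will "compare each immune parameter (changes in magnitude of VZV-specific B cells and the kinetics of these changes) between D7, D14, D30, D180 and D270"+ on one side and D0 on the other, for each dose.

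Section 13.7 (Sample Size Considerations) sizes two relevant tests. One begins "For unpaired test, with sample size of 30 per group, at the alpha level of 0.01", with 80% power at 0.91 SD. The other begins "For a paired t-test, with the sample size of 30, at the alpha level of 0.01", with 80% power at 0.66 SD. Neither is tied to a numbered endpoint.

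**The concern.** A paired test against D0 asks whether a cell measure changed after vaccination. It says nothing about whether the change differs between two independent cohorts, which is what these two objectives ask. If the plan is followed as written, it yields tests of change and no estimate of the age difference, with no confidence interval for it. The reader of the results would have no planned analysis to set against two stated objectives, although the samples will have been taken and a suitable test has already been sized.

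**Working it through.** **1. Is the contrast assigned anywhere in 13.4?** The candidates are:

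- 13.4 (introduction): PCA, PLSDA, clustering and factor analysis serve visualization and global patterns. The separate analysis of the age groups is stated for innate signatures. Neither gives an age contrast for VZV-specific cells.
- 13.4.4: Fisher's exact test is the only inferential between-group test named. It stands in a paragraph about AE rates and does not suit continuous cell measures.
- 13.4.5, Endpoints 5 and 6: tests against D0 only.
- 13.4.5, closing paragraph: other approaches are allowed ad hoc, but no age contrast is named.
- 13.4.6: visual displays by group cover antibody titers only.

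Number of between-cohort comparisons assigned to Endpoints 5 and 6: none.

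**2. Inputs.** n = 30 per cohort (3.1, 3.5, 13.1); two-sided alpha 0.01, equal variance, and effect sizes of 0.91 and 0.66 SD (13.7). Assumptions: the SD is that of the change from baseline and is equal in both cohorts. As the documents give no dropout rate, and 11.3 does not replace subjects once dosed, 27 evaluable per cohort is used as an assumed case.

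**3. Reproduce the unpaired figure in 13.7.** Power = P(T > t(0.995, 2n−2)), where T is noncentral t with 2n−2 degrees of freedom and noncentrality d·√(n/2); the opposite tail is negligible.

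- n = 30, d = 0.91: noncentrality = 0.91 × √15 = 3.524; critical value 2.663 on 58 df; power 80.2%. The exact detectable difference at 80% power is 0.909 SD. The plan's 0.91 is correct.

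**4. Reproduce the paired figure, and see which sample it describes.** Noncentrality d·√n, n−1 degrees of freedom.

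- n = 30, d = 0.66: noncentrality = 0.66 × √30 = 3.615; critical value 2.756; power 79.7%; detectable 0.662 SD.
- n = 60: detectable 0.454 SD.

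The plan's 0.66 therefore belongs to one cohort of 30, not to the pooled 60. This suggests that the paired tests are meant per cohort, though 13.4.5 does not say so for Endpoints 5 and 6.

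**5. What the two-sample test could show if assigned.** Alpha 0.01 without further adjustment:

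| Evaluable per cohort | True difference (SD of change) | Noncentrality | Power |
|---|---|---|---|
| 30 | 0.91 | 3.524 | 80.2% |
| 30 | 0.66 | 0.66 × √15 = 2.556 | 46.3% |
| 30 | 0.50 | 0.50 × √15 = 1.936 | 24.4% |
| 27 (assumed) | 0.91 | 0.91 × √13.5 = 3.344 | 74.6% |

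With 27 per cohort, the detectable difference at 80% power is 0.96 SD. With 30 per cohort, the 95% CI half-width is t(0.975, 58) × √(2/30) = 2.002 × 0.2582 = 0.517 SD.

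**6. Number of contrasts.** The fixed days for these cells are 7, 14 and 30 days after each dose (D7, D14, D30, D67, D74, D90) plus D180: 3 + 3 + 1 = 7 per parameter. D270+ is not a fixed day: "An optional visit at any time point past 9 months (D270 +) from first vaccination may also take place".

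**The case against.** The strongest reply is that the comparison was planned. The study has exactly two groups of 30, so an unpaired test sized on 30 per group can only be the age contrast. Section 13.7 supplies its alpha, sidedness and detectable effect, and it maps none of its other calculations to numbered endpoints either. Both objectives are exploratory, and 13.4.5 openly reserves room for other methods.

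Much of this stands. A reader might infer that the authors never foresaw an age comparison; 13.7 does not support that. What is missing is the assignment. Section 13.7 does not say which parameters, days, baseline or multiplicity rule the test applies to, and 13.4.5, where the analysis is laid down, gives these endpoints a different test. The ad hoc allowance permits a cohort comparison but does not commit to one.

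A reader might also infer that FDR control governs these cell measures, because 13.7 says "In actual data analysis false discovery rate (FDR) will be used". That sentence closes the argument about roughly 20,000 genes, and the next paragraph again ties FDR to gene expression. For immune parameters, 13.7 gives alpha 0.01 with fewer than 50 tests and less than one expected false positive. The text does not establish that FDR extends to T and B cells, so no detectable differences under FDR are given here.

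It is also fair to say that day-by-day two-sample tests would not fully answer the objectives, which name kinetics as well as magnitude. The fix has to cover that.

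**Conclusion.** The point holds as a gap between objectives, analysis and sizing: two exploratory objectives have no assigned between-cohort analysis, and the test that fits them is sized but not assigned. It is not an arithmetic error, since the paired and unpaired figures in 13.7 reproduce. It does not touch the primary or secondary endpoints and calls for no change in sample size. It should be corrected, in proportion to the exploratory status of the objectives.

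A reader might infer that age effects will be read off from significance in one cohort and not in the other. The documents do not say this will be done, and the point does not rest on it.

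The power figures assume normal changes with equal SD, 30 evaluable per cohort unless stated otherwise, and alpha 0.01 per test. Under these assumptions a direct comparison is informative only for large differences, so the estimate and its interval matter more than the p-value.

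**What to change.** In 13.4.5, for Exploratory Endpoints 5 and 6:

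- State that the paired tests are run within each cohort.
- Add a direct between-cohort comparison of change from baseline at D7, D14, D30, D67, D74, D90 and D180. Use the two-sample t-test already sized in 13.7, or a rank-sum test with a shift estimate, and report the difference with its CI.
- Address kinetics with a cohort-by-time term in a repeated-measures model, or with a prespecified summary across days.
- Keep D270+ descriptive, because the visit is optional and its timing open-ended.
- Clarify whether the dose-2 baseline is D0 or D60. Section 13.2 takes D0 as pre-vaccination, while 13.4.5 refers to D0 for each dose.
- State the multiplicity rule for these parameters: alpha 0.01, as 13.7 gives for immune parameters, or FDR if that is intended.
- Note that the cohorts are defined by age and not randomised, so the result is an unadjusted age-group association.

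In 13.7, name these endpoints as the use of the unpaired calculation.

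Cost: SAP wording and modest extra analysis of data already to be collected. The downsides are a larger test family (seven day-specific contrasts per parameter, plus the kinetics analysis) and power only for large differences: 0.91 SD with 30 per cohort, or 0.96 SD if 27 are evaluable (assumed).
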